Prior to recruitment, the lead investigator (DB) and one of the study investigators (SS) set up a report in ScholarOne that shows a list of original research submissions to BMJ Open, including their ID, date of submission, title, abstract, and different parameters related to their peer review status. This report will be automatically sent on a daily basis to the lead investigator (DB), who will daily check it for randomised trials (based on given title and abstract) meeting our inclusion criteria.

Recruitment of manuscripts started in 7th December 2018.

Sample size (SPIRIT i14, SAP i11)

In order to estimate the proportion of adequately reported items in the control group, the lead investigator (DB) performed a pilot evaluation of 12 random randomised trials published in BMJ Open between April 2018 and September 2018, which was verified by the two CONSORT experts (EC and JJK). According to it, the estimated probabilities of the manuscripts in the control group adequately reporting (0, 1, 2, ..., 8) items would be (0, 0, 0, 0, 0, 0.17, 0.33, 0.33, 0.17).

If we expect the intervention to manuscripts in the intervention group adequately report 7 and 8 items 50% and 50% of the times, respectively, a sample size of 24 articles (12 per arm) would be enough to detect such increase with 85% of power.

To relax the strong assumptions behind the t-test, which was initially used, we re-defined the main analysis and used bootstrapping calculations (see “Statistical methods” section and Box 3), after which we checked that the power did not decrease (see Box 2 for the final power calculation).

Box 2: Power calculation

```
na = 12
nb = 12
A = 0:8
B = 0:8
pra = c(0,0,0,0,0,0,0,5,5)
pra = pra/sum(pra)
prb = c(0,0,0,0,0,2,4,4,2)
prb = prb/sum(prb)
nboot <- 1000
N = 1000
ma = matrix(sample(A, pr=pra, replace=TRUE, siz=N*na), ncol=N)
mb = matrix(sample(B, pr=prb, replace=TRUE, siz=N*nb), ncol=N)
sign1 <- c()
for (i in 1:N) {
  reporting <- data.frame(
    score = c(ma[,i],mb[,i]),
    group = factor(rep(c("Control", "Intervention"), c(na, nb)))
  )
  diff.mean1 <- c()
  for (k in 1:nboot){
    sel <- sample(1:(na+nb),na+nb,rep=TRUE) # selected articles
    reporting.boot <- reporting[sel,]
    diff.mean1[k]<- with(reporting.boot,diff(tapply(score,group,mean)))
  }
  conf.int1 <- quantile(diff.mean1,c(0.025,0.975))
  sign1[i] <- conf.int1[1]>0 | conf.int1[2]<0
}
sum(sign1)/N
```

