For the primary outcome, we will adjust a linear regression model with the baseline percentage of consistency between the manuscript and the checklist as the only covariate. The 95% confidence interval will be calculated using bootstrapping (see Box 3).

In case that we have missing data for the primary outcome for some of the manuscripts included, the scores will be imputed with a value of $1-b$, where b is the baseline score of the manuscript, regardless of the manuscript allocation. This would reflect that rejecting a manuscript with low baseline score could be considered as an editorial success. Multiple imputation of missing values was discarded because missingness could not entirely be due to observed variables (18). For example, a manuscript with excellent reporting quality could be rejected based on other reasons, such as poor methodological quality or the fact that it does not meet the scope of the journal. Secondly, the robustness of the primary outcome results will be assessed by carrying out the complete case analysis.

Box 3: Primary outcome analysis (*The file 'Primary outcome analysis.txt' contains the baseline and final scores of each paper, as well as its allocation*)

```
data <- read.csv2('Primary outcome analysis.txt', header = TRUE, sep = '')
model1 <- lm(data$Final ~ data$Baseline + data$Group)
summary(model1)
na=12
nb=12
nboot <- 1000
diff.mean1 <- c()
for (k in 1:nboot){
  sel <- sample(1:(na+nb),na+nb,rep=TRUE) # selected articles
  reporting.boot <- data[sel,]
  diff.mean1[k] <- coefficients(lm(reporting.boot$Final ~
reporting.boot$Group + reporting.boot$Baseline,reporting.boot))[2]
}
conf.int1 <- quantile(diff.mean1,c(0.025,0.975))
```

Data monitoring (SPIRIT i21)

The study will not have a formal data monitoring committee.

Harms (SPIRIT i22)

Not described.

Auditing (SPIRIT i23)

The trial will not be externally audited.

Research ethics approval (SPIRIT i24)

Ethics approval has been obtained from the Research Committee of the Governing Council of the Universitat Politècnica de Catalunya (UPC). Ref: EC 02. Date: 13 September 2018.

Protocol amendments (SPIRIT i25)

Any important protocol amendments will be registered at ClinicalTrials.gov and communicated in the primary RCT report.

Consent or assent & informed consent materials (SPIRIT i26 & i32)

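### The primary 95% interval in Box 3 is an uncorrected percentile bootstrap on 24 manuscripts and covers about 93% in settings close to the pilot data

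*Combined protocol and SAP*

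**What the plan says.** The Statistical methods section specifies a linear regression of the final score on group, adjusted for baseline, and says of its interval: "The 95% confidence interval will be calculated using bootstrapping (see Box 3"). Box 3 fits that regression once to the observed data ("model1 <- lm(data$Final ~ data$Baseline + data$Group"). It then resamples the 24 manuscripts without regard to arm ("sel <- sample(1:(na+nb),na+nb,rep=TRUE) # selected articles"), refits 1000 times and reads off the raw quantiles ("conf.int1 <- quantile(diff.mean1,c(0.025,0.975"). The fitted regression is summarised, but its t interval is not the specified one. No seed is set.

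The Sample size section gives the reason for this choice: "To relax the strong assumptions behind the t-test, which was initially used, we re-defined the main analysis and used bootstrapping calculations". The check it reports is that "after which we checked that the power did not decrease". It reports no check of coverage or of the false-positive rate.

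The text states no significance rule. The only one is in the power code of Box 2, which counts a simulated trial as positive when the percentile interval excludes zero: "sign1[i] <- conf.int1[1]>0 | conf.int1[2]<0".

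For missing primary outcomes, "the scores will be imputed with a value of" 1-b, where b is the manuscript's baseline score.

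**The concern.** The percentile bootstrap is justified for large samples. With 24 rows and three regression coefficients it understates uncertainty in two ways. The resampled residual variation is not inflated for the fitted parameters, and the percentile limits behave like normal rather than t quantiles. The bootstrap was adopted to relax assumptions, so it may introduce a coverage error where the t interval had almost none.

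The power check cannot show this. An interval that is too narrow excludes zero more often whether or not there is an effect, so the fault appears as a gain in power. At stake is the precision statement for the primary result and, if the Box 2 rule is applied, the trial's false-positive rate.

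**Working it through.** **Inputs from the plan.** 12 manuscripts per arm. Control scores of 5, 6, 7 and 8 items in the ratio 2:4:4:2 (mean 6.5, SD 0.957). Intervention scores of 7 or 8 items, half each (mean 7.5, SD 0.5). 1000 resamples; regression on group and baseline, so 24 - 3 = 21 residual degrees of freedom.

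**Assumed, because the plan does not give it.** How final scores arise from baseline scores, the baseline distribution (taken from the pilot unless noted), and the amount of missing data (missing at random).

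**1. The stated power.** Pooled SD = sqrt((0.957² + 0.5²)/2) = 0.764, for a difference of 1.0 item. Power is 86.5% from the noncentral t (86.6% simulated) and 85.3% for a simulated Welch test. The stated 85% is reproduced.

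**2. Why the interval is narrow.** A rough ratio to the t interval is sqrt(21/24) × 1.960/2.080 = 0.935 × 0.942 = 0.88. Because resampling is not stratified, arm sizes and baseline spread vary between resamples, which recovers part of the loss. Simulation gives about 0.93.

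**3. How often the interval excludes zero when there is no effect.** Box 3 was re-run on 16,000 simulated trials per setting (Monte Carlo SE about 0.2 points; 4,000 trials for the wider baseline).

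| Setting | Box 3 percentile | Regression t(21) | Coefficient ± t(21) × bootstrap SD |
|---|---|---|---|
| Final redrawn from pilot | 6.6% | 5.4% | 5.6% |
| 50% of scores unchanged | 7.1% | 4.8% | 5.6% |
| Each missing item fixed with probability 0.3 | 6.9% | 5.2% | 5.1% |
| Same, probability 0.5 | 6.9% | 5.2% | 5.3% |
| Gaussian data | 7.3% | 5.2% | 5.4% |
| 80% unchanged | 4.4% | 2.7% | 2.6% |
| Fixed with probability 0.10 | 3.3% | 3.5% | 3.1% |
| Fixed with probability 0.05 | 0.7% | 1.5% | 1.0% |
| Wider baseline (uniform, 1 to 8 items), 80% unchanged | 6.1% | 2.45% | 2.45% |
| 15% imputed as 1-b: redrawn | 7.4% | 4.7% | 4.8% |
| 15% imputed: 50% unchanged | 8.2% | 4.8% | 4.8% |
| 15% imputed: 80% unchanged | 8.2% | 4.1% | 4.0% |
| 15% imputed: fixed 0.3 | 8.4% | 4.0% | 3.8% |
| 15% imputed: fixed 0.5 | 8.8% | 4.3% | 4.2% |
| 5% imputed: fixed 0.3 | 8.0% | 2.8% | 2.5% |
| 25% imputed: fixed 0.3 | 7.0% | 4.5% | 4.7% |

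Imputation creates outliers: a pilot baseline of 5 to 8 items out of 8 gives an imputed final of 3 down to 0 items, well below the observed scores.

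**4. At the planned effect.** In the same order of intervals, coverage is 93.2%, 94.5% and 94.3%, and power is 88.6%, 85.2% and 85.1%. The median width of the percentile interval is 0.932 of the t interval.

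**5. Sensitivity to the link between baseline and final.** A second simulation used an assumed latent correlation (5,000 to 10,000 trials per setting).
- No effect, correlation 0 to 0.9: percentile coverage 92.4 to 94.0%, mean width ratio 0.933 to 0.942.
- Planned effect, correlation 0 to 0.7: coverage 92.9 to 93.4% against 94.2 to 95.0% for the t interval, width ratio 0.933 to 0.948.
- Wider baseline: width ratio up to 0.951.

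**6. The plan's own power check.** Box 2 as written (4,000 trials) gives 89.5% power against 86.9% for the t-test. With no effect it rejects in 6.1% of trials against 5.2%. Part of the apparent gain in power is therefore excess false positives.

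**7. Resampling noise.** Two unseeded runs of 1000 resamples disagree on whether zero is excluded in 1.2% (no effect) to 2.2% (planned effect) of trials. With 10,000 resamples this falls to 0.3 to 0.8%.

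**The case against.** The shortfall is about 1.5 to 2 points of coverage in a 24-manuscript trial, and the Statistical methods text plans an interval, not a test. Its size, and even its direction, depend on how scores change between versions, which the plan cannot settle: the null rates for the Box 3 interval run from 0.7% to 8.8%. Few changes are plausible under a null, since control manuscripts receive only usual peer review, and in most such settings the planned interval is conservative. The pilot scored published articles, so using it for baseline scores of submitted manuscripts is an approximation. Redrawing finals independently of baseline is also unlikely for the same manuscript scored twice. Nor do the corrected intervals hit 5% everywhere. With 80% unchanged they sit near 2.7%, against 4.4% for the planned interval; with the wider baseline they are at 2.45% against 6.1%. In both cases the planned interval is nearer 5%.

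Much of this stands. The claim must be limited to settings near the pilot data, and the narrowing is better given as 5 to 7% across settings. The second simulation did not include mostly unchanged scores, so it says nothing about those cases.

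It does not rescue the method. The excess persists across the other ways of generating final scores and with Gaussian data. The protection from few changes also disappears with imputation: at 80% unchanged, 15% imputed scores move the planned interval from 4.4% to 8.2%. Where the corrected intervals depart materially from 5%, they do so on the conservative side.

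**Conclusion.** The concern holds. In settings close to the pilot data, the primary interval is 5 to 7% narrower than the t interval and covers about 93%, where the t interval stays close to 95% on the same discrete scores. Read as a test, it runs at 6.6 to 7.1% there, and at 7.4 to 8.8% if 15% of finals are imputed as 1-b at random. The error is modest and not uniform: where few scores change and none are imputed, it mostly reverses. These figures rest on the pilot distribution and on assumed links between baseline and final scores. Nothing else in the plan corrects the interval. The change is worth making because it costs little, but the fault does not by itself threaten the trial.

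**What to change.** Replace the raw percentile limits in Box 3 by one of these two, and name it in the text as the primary interval:

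- To keep resampling: the group coefficient plus or minus the t quantile times the bootstrap standard deviation, i.e. `coef(model1)[3] + c(-1,1) * qt(0.975, df.residual(model1)) * sd(diff.mean1)`. Group is the third coefficient in the regression as Box 3 fits it. The residual degrees of freedom are 21 with all 24 manuscripts and fewer in the complete-case analysis.
- Otherwise: `confint(model1)`, the t interval from the regression already fitted.

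State in the Statistical methods section whether excluding zero is the decision rule. Keep the percentile interval as a sensitivity analysis, with `set.seed` and about 10,000 resamples.

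The cost is one or two lines of R and a short addition to the text. The interval becomes about 7% wider (1/0.932 = 1.07). Simulated power at the planned effect is 85.1 to 85.2%, in line with the stated 85%, so the sample size need not change.

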Assignment of interventions (SPIRIT i16 & i17, SAP i10 & i24) [sequence generation, allocation concealment mechanism, implementation, blinding]

Every time the lead investigator (DB) detects in the submissions report a randomised trial that has at least one peer reviewer invited, he will transfer a PDF version of it to a BMJ Google Drive folder. The randomisation process of the manuscript will be performed using a Shiny applicative (R Software) created by one of the study collaborators (JAG). The lead investigator will introduce the manuscript ID into the applicative, which will randomise it with a 1:1 allocation ratio in blocks of 4. Moreover, manuscripts will be stratified according to whether there is an applicable extension for that study or not. An email will be received by the lead investigator indicating the manuscript allocation. To avoid selection bias, the applicative will only allow to introduce each manuscript ID once and will record the times when the allocation was performed.

The folder containing the manuscript allocations and PDFs will remain unavailable to authors of included manuscripts and outcome assessors, who will be masked to allocation. *Every time the lead investigator (DB) detects that an editorial decision has been made on a manuscript and that authors have revised it, he will first make available to the outcome assessors (JJK, EC) the first submitted version of the manuscript. Then, they will have to complete the evaluation form for the manuscript independently and in duplicate. This form will include the CONSORT extensions to be used. Once this is done, DB will inform the outcome assessors of the discrepancies, if any, so that they can solve them by consensus via Skype call and agree on a final joint score. Afterwards, DB will share the first revised manuscript and the outcome assessors will evaluate it. Again, DB will point out discrepancies, they will solve them and assign a final score to the manuscript.*

Due to the nature of the intervention, handling editors of the included manuscripts and the lead investigator assessing the reporting inconsistencies (DB) cannot be blinded.

Data management (SPIRIT i19)

All data related to the study *is being collated* in a password protected spreadsheet file stored in Google Drive.

Statistical methods (SPIRIT i20, SAP i25, i27, i28 & i31)

Statistical analysis will be carried out using R software.

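### The primary 95% CI rests on 1000 unseeded bootstrap draws, which leaves a small, avoidable simulation error in each limit

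*Combined protocol and SAP*

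**What the plan says.** The Statistical methods section sets a linear regression of the final score on group and baseline, and adds: "The 95% confidence interval will be calculated using bootstrapping (see Box 3". On software it says only: "Statistical analysis will be carried out using R software".

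Box 3 then prints the script. It fits the model once and calls `summary(model1)`, sets `nboot` to 1000, and in each pass resamples the 24 manuscripts with "sel <- sample(1:(na+nb),na+nb,rep=TRUE) # selected articles". It keeps the group coefficient each time and ends with the percentile limits, "conf.int1 <- quantile(diff.mean1,c(0.025,0.975". No seed is set in Box 3, in Box 2 or in the text, and nothing says which run is to be reported.

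The Statistical methods section gives no significance rule in words. The only one in print is in the power code in Box 2, which counts a trial as positive by "sign1[i] <- conf.int1[1]>0 | conf.int1[2]<0".

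**The concern.** A 2.5% quantile of 1000 draws has only about 25 draws beyond it. The limit therefore has simulation error on top of sampling error, and the same script on the same 24 rows returns slightly different limits each time. If the conclusion follows Box 2's criterion, a limit very near 0 can fall on either side depending on the run. This does not depend on whether a percentile interval has the right coverage: any interval built from 1000 unseeded draws shares the problem. At stake are the last digits of the primary interval and, in a small share of possible datasets, whether it excludes 0.

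**Working it through.** **1. The plan's own figure.** Box 2 has intervention manuscripts scoring 7 or 8 with equal probability (mean 7.5, variance 0.25). Controls follow "prb = c(0,0,0,0,0,2,4,4,2", that is 5, 6, 7, 8 at 2:4:4:2, with mean 78/12 = 6.5 and variance 11/12 = 0.917. The root-mean-square SD is √((0.25 + 0.917)/2) = 0.764. With 12 per arm, the noncentral t (22 df) gives 86.5% power, simulated t-tests give 86.8% (pooled) and 85.5% (Welch), and the Box 2 bootstrap with 1000 draws gives 89.9%. The plan states that "a sample size of 24 articles (12 per arm) would be enough to detect such increase with 85% of power" and that power did not fall with the bootstrap. Both statements reproduce.

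**2. Simulation error of a limit.** In units of the bootstrap SE, the Monte Carlo SD of a 2.5% quantile from B draws is √(0.025 × 0.975 / B) / φ(1.96), with φ(1.96) = 0.0584.

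- B = 1000: 0.00494 / 0.0584 = 8.4% of the SE. Two runs then differ by up to about 1.96 × √2 × 8.4% = 0.23 SE (95% range).
- B = 10,000: 2.7%.
- B = 50,000: 0.000698 / 0.0584 = 1.2%.
- B = 100,000: 0.8%.

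The bootstrap SE in the four simulated datasets below was 0.0281 to 0.0393 on the proportion scale. At B = 1000 the SD of a limit is therefore about 0.0024 to 0.0033. At B = 50,000 it is about 0.0003 to 0.0005.

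**3. Repeated runs of Box 3 on fixed data.** Four simulated datasets were used, three of them picked because the lower limit lies near 0. There were 2000, 400 and 40 runs at the three values of B.

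| Lower limit (200,000 draws) | SD of lower limit, B = 1000 | Runs excluding 0, B = 1000 | B = 10,000 | B = 100,000 |
|---|---|---|---|---|
| +0.0012 | 0.0026 | 67% | 87% | 100% |
| +0.0011 | 0.0036 | 66% | 86% | 100% |
| −0.0017 | 0.0025 | 27% | 2% | 0% |
| +0.0268 | 0.0030 | 100% | 100% | 100% |

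**4. How often two runs disagree on excluding 0.** This needs an assumed dependence between baseline and final score, because the documents give none. All figures use Box 2's planned effect unless stated.

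- Box 2 analysis without baseline: 1.8% of trials at B = 1000, 0.4% at B = 10,000.
- Box 3 analysis at B = 1000, with the final score tied to baseline with probability 0, 0.5 or 0.8: 2.0%, 0.8% and 0.4%.
- Box 3 analysis in further simulations with assumed baselines: 0.9% to 2.0%; with a moderately correlated baseline and no effect, 0.9%.

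**5. Visible change in the reported interval.** At B = 1000, at least one limit changed at two decimals between two runs in 52% to 59% of trials.

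**The case against.** The strongest reply is that the error hardly matters. An SD of 0.003 is about 0.003 × 8 = 0.02 of one item. If a limit's sampling SD is taken as about one SE, adding 8.4% of an SE in quadrature raises it by √(1 + 0.084²) − 1, about 0.4%. Average coverage and power are essentially untouched. In the clear dataset above every run excluded 0. `summary(model1)` also gives an estimate, SE and p-value that do not change between runs. All of this stands, and it is why the point is small. It does not show that the error should be kept, since it can be cut sharply at almost no cost.

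Three stronger readings are tempting, and the documents do not support them.

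- A reader might infer that the missing seed stops outsiders from reproducing the published interval. The section on dissemination and access to data says no dataset with individual manuscript data will be released, so outsiders could not do so even with a seed. The gain is for the team's own checks on the stored files.
- A reader might infer that an unblinded team could keep the more favourable of two runs. Nothing in the documents suggests several runs or a choice among them.
- A reader might infer that the run decides the trial's conclusion. That needs a limit very near 0, and a decision rule that appears only in the power code.

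**Conclusion.** The concern holds as a minor point about precision and repeatability. That each limit carries Monte Carlo error of about 8% of the bootstrap SE follows from the printed number of draws alone. The SD of about 0.003 also uses simulated bootstrap SEs. The 0.4% to 2% disagreement on 0, and the change at two decimals in roughly half of trials, rest on Box 2's score distributions and on assumed dependence between baseline and final score. They should be quoted as ranges.

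Two limits on the remedy matter. A seed alone freezes one arbitrary run at 1000 draws and adds no precision. Nor does a modest increase settle everything: at 10,000 draws, two of the three borderline datasets still gave the minority answer in about one run in seven (13% and 14%). More draws shrink the band around 0 in which the answer can change, but no finite number removes it.

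**What to change.** In Box 3:

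- Change `nboot <- 1000` to `nboot <- 50000` or more. This brings the SD of each limit down to about 0.0005 or less.
- Put `set.seed()` before the loop, with a number written into the plan before the analysis.
- Use the same seed and number of draws for the complete-case analysis, with `na` and `nb` set to the manuscripts in it.
- State that this single run is the one reported.

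The cost is two lines of code and 50 times as many fits of a small regression to 24 rows. The running time in R was not measured, but should be only slightly longer. The estimand, the model and the sample size do not change.

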The intervention will consist of three steps that have been co-designed with the BMJ Publishing Group. First, the completed CONSORT checklist submitted by authors of manuscripts randomised to the intervention group will be assessed by the lead investigator (DB) as to whether it is consistent with the information that was actually reported in the manuscript. To determine what information authors are expected to report, we will rely on the CONSORT Explanation and Elaboration document (15) or the corresponding Explanation and Elaboration documents for each of the extensions considered (5–14). In a second step, the lead investigator (DB) will produce a standardised report containing precise requests to be addressed by authors in order to improve the completeness of reporting of the items where reporting inconsistencies were found. This report will consist of a brief introduction followed by a point by point description of the inconsistencies found together with precise requests related to the information missing and examples extracted from CONSORT (see an example in Box 1). The lead investigator (DB) will upload this report to the submission on the managing system of the journal (ScholarOne) to make it accessible to the handling editor of the manuscript. Finally, this editor will include our report in the letter to authors alongside the standard peer review reports. Manuscripts randomised to the control group will undergo the usual peer review process. Figure 1 describes the manuscript flow of the study.

Our intervention has not been previously evaluated (16). One potential facilitator of the intervention is that it can be implemented and evaluated in a real editorial context with no disruption to normal manuscript submission, peer review and editorial procedures.

[figure not shown]
Box 1. Example of report on the reporting inconsistencies found

This report shows the results of an evaluation of the consistency between the CONSORT checklist you submitted and the information that was reported in the manuscript.

Please, make the following revisions:

- *For CONSORT Item 8a (“Method used to generate the random allocation sequence”), please report the method used to generate the random allocation sequence.*
 - *Example from CONSORT: “Randomization sequence was created using Stata M.N (StataCorp, College Station, TX) statistical software”.*

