- **Primary outcome:** Proportion of adequately reported items in the first revised manuscript [Time frame: Following manuscript revision (usually 2-3 months)]. An item will be considered as adequately reported if all subparts of the item (including all possible extensions, where relevant) are adequately reported [e.g. for CONSORT item 6a: A) completely prespecified primary and secondary outcomes, B) how each of these outcomes is assessed, and C) when each of these outcomes is assessed].
- **Secondary outcomes:** i) Proportion of manuscripts where each item is adequately reported [Time frame: Following manuscript revision (usually 2-3 months)], and ii) Average time to perform the assessment of reporting inconsistencies and to produce the report [Time frame: Following the evaluation of reporting inconsistencies by the lead investigator (1 week)].

Outcome evaluation will be performed independently and in duplicate by two masked outcome assessors (EC, JJK) with extensive experience in reporting and methodological issues of randomised trials. Outcome assessors will also collect baseline measures of compliance between the CONSORT checklist and the manuscript in order to adjust for these in the analysis (see "Statistical methods" section). [Outcome evaluation will start on 17 May 2019](#).

To ensure that the evaluations of the two outcome assessors are consistent, they appraised 6 random randomised trials published in BMJ Open between April 2018 and September 2018. Discrepancies among evaluators were discussed.

We consider two potential scenarios that could lead to missing data on the study outcomes: (i) when a manuscript is rejected after peer review and therefore not returned to authors for revision, and (ii) when authors do not return the revised manuscript within the established time (28 days plus, if necessary, the extra time that the handling editor of each manuscript considers appropriate) after a “Minor revision” or “Major revision” editorial decision. Methods to handle missing data are reported below (see “Statistical methods” section).

Participant timeline and recruitment (SPIRIT i13 & i15, SAP i21)

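### Imputing a missing revised score as 1 − b in the primary analysis counts a well-reported manuscript that is rejected or not returned as poorly reported

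*Combined protocol and SAP*

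**What the plan says.** The primary outcome (Outcomes section) is the share of the eight core CONSORT items that the first revision reports adequately. The section foresees two ways of losing it: the manuscript is rejected following review, or the loss arises "when authors do not return the revised manuscript within the established time". For both, Statistical methods states that "the scores will be imputed with a value of $1-b$, where b is the baseline score of the manuscript, regardless of the manuscript allocation". The reason offered is that "rejecting a manuscript with low baseline score could be considered as an editorial success". Multiple imputation is set aside because missingness may depend on unobserved factors; the example is that "a manuscript with excellent reporting quality could be rejected based on other reasons, such as poor methodological quality". As a second step, "the robustness of the primary outcome results will be assessed by carrying out the complete case analysis". Box 3 regresses the final score on group and baseline score and takes a percentile-bootstrap 95% interval for the group coefficient.

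Three other statements bear on this:
- Under Outcomes, "Outcome assessors will also collect baseline measures of compliance between the CONSORT checklist and the manuscript".
- Under Assignment of interventions, the assessors receive the first submitted version once there is an editorial decision and the authors have revised.
- Under Interventions, the report on inconsistencies is uploaded "to make it accessible to the handling editor of the manuscript". Editors are stated to be unblinded.

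**The concern.** The rule replaces an unknown reporting score by the mirror image of the manuscript's own baseline. Any missing manuscript above 4/8 is scored below the only version that exists, and any below 4/8 is scored above it. Editorial success is neither the declared outcome nor the stated objective. As a justification it covers one case, the rejection of a poorly reported manuscript. It does not cover a well-reported manuscript rejected for methods or scope, and it has no bearing on a revision that was invited but never came back.

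The trial has 24 manuscripts and the sample size states no allowance for missing scores, so one or two imputed values can move the headline result. If losses are spread evenly, the main harm is lost precision. If they fall mainly in one arm, the estimate is biased and the arm sets the direction. Unequal loss is possible because unblinded editors can see the intervention report when they decide.

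**Working it through.** **Inputs.** Eight items and 12 manuscripts per arm. The Box 2 control distribution (5, 6, 7, 8 items with weights 2, 4, 4, 2) has mean (10 + 24 + 28 + 16)/12 = 6.5 items and SD 0.957. The intervention distribution (7 or 8 items, 50% each) has mean 7.5 and SD 0.5. The planned effect is therefore 1 item, or 0.125 on the proportion scale. I take b to be the baseline proportion of the eight items adequately reported.

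**The plan's own figure.** A simulated two-sided Welch t-test gives 85.4% power and the Box 2 bootstrap 89.3%. The stated 85% is reproduced, and the bootstrap does not lower it.

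**What the rule does to one score.**

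| Baseline | 8/8 | 7/8 | 6/8 | 5/8 | 4/8 | 2/8 | 0/8 |
|---|---|---|---|---|---|---|---|
| Imputed | 0 | 0.125 | 0.25 | 0.375 | 0.5 | 0.75 | 1 |

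**Shift of an arm mean per missing manuscript**, in items, against its expected final score: (8 − 8b − expected final)/12.

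| Mean baseline | Control | Intervention |
|---|---|---|
| 6.5/8 (pilot) | (1.5 − 6.5)/12 = −0.42 | (1.5 − 7.5)/12 = −0.50 |
| 4.5/8 | (3.5 − 6.5)/12 = −0.25 | (3.5 − 7.5)/12 = −0.33 |
| 3.5/8 | (4.5 − 6.5)/12 = −0.17 | (4.5 − 7.5)/12 = −0.25 |

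The lower baselines are assumptions. The only source in the documents is the "pilot evaluation of 12 random randomised trials published in BMJ Open between April 2018 and September 2018", and submitted manuscripts may be less well reported than published ones.

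**Expected estimates, true effect 1 item.** One intervention loss gives 1 − 0.50 = 0.50 to 1 − 0.33 = 0.67; two give 0 to 0.33. One control loss gives 1.25 to 1.42; two give 1.50 to 1.83. With k of 24 missing at random, the imputed scores have the same mean in both arms, so the expected effect is 1 − k/24: 0.96, 0.92 and 0.83 for k = 1, 2 and 4.

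**Simulation of the Box 3 model** (1,500 trials per setting, 500 resamples, Monte Carlo error about 2.5 points). The main range covers three baselines: the pilot distribution independent of the final score; the pilot distribution with the final score tied to baseline; and the pilot distribution minus two items, independent. The last column is the pilot minus three items, independent.

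| Missing | 1 − b: mean estimate; power | Three items lower |
|---|---|---|
| None | power 87–100% | |
| 1 of 24 at random | about 0.97; 51–59% | 67% |
| 2 at random | about 0.92; 29–42% | 53% |
| 4 at random | about 0.83; 18–28% | 41% |
| 1 intervention | 0.50–0.67; 5–23% | 0.75; 43% |
| 2 intervention | 0–0.33; 0–2% | 0.50; 12% |
| 1 control | 1.25–1.41 | |
| 2 control | 1.50–1.84 | |

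Complete case on the same data keeps at least 84% power with 2 missing at random and 80% with 4. Its estimate stays near 1.0 item in the one-arm settings. With exactly one loss per arm and the final score independent of baseline, power under 1 − b is about 13% at the pilot mean, 22% one item lower and 54% three items lower, against 84–86% for complete case.

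**No true effect, two losses in one arm.** The estimate shifts by 0.49–0.84 item (0.33 at three items lower). The interval excludes zero in 13–19% of trials if the final score is independent of baseline (6% with none missing), and in 0% if it equals baseline.

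**Rejection that depends on baseline, two intervention losses, true effect 1 item** (1,200 trials per setting).

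| Lost | Complete case | 1 − b | 1 − b, three items lower |
|---|---|---|---|
| Two lowest baselines | 0.90–1.00 | 0.18–0.54 | 0.71 |
| Two highest baselines | 0.99–1.10 | −0.30 to 0.12 | about 0.27 |

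**The case against.** The rule is deliberate, prespecified and the same in both arms. It can be read as a composite in which rejecting a poorly reported manuscript counts as success. Complete case is already planned, so a distorted result would show as disagreement between the two. With equal losses and no true effect, the rule does not bias the difference on average. The harm depends on losses whose rate the documents do not give, the worst figures need both losses in the intervention arm, and nothing shows that seeing the report changes editors' decisions. All of this stands as a limit on size. It does not rescue the rule, because the composite reading fails for well-reported rejections and for unreturned revisions, and a planned second analysis does not repair the headline one.

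The strongest objection is that complete case conditions on a decision taken after randomisation by an unblinded editor. With no true effect, suppose the two intervention manuscripts with the lowest unseen final scores are lost. Complete case then gives +0.25 item and an interval excluding zero in 14% of trials; 1 − b gives −0.29 to −0.61 item and 4–7%. At three items lower, complete case gives +0.26 item and about 15%, while 1 − b gives −0.12 item and 5%, so there 1 − b does better on both counts. Complete case is therefore not uniformly safer, and the plan must say so. In the other settings tested with a true effect it stayed close to the truth, and 1 − b did not when losses fell in one arm.

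Two attached points are minor. Box 3 is correct for 24 imputed rows, and on a shorter file R still returns an interval, but from resamples that include absent rows. The workflow under Assignment of interventions does not say that unrevised manuscripts go unscored; it leaves this open.

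**Conclusion.** The concern holds, and the primary analysis should be changed. The rule gives scores that contradict the declared outcome for well-reported rejections, and it has no stated basis for unreturned revisions. One intervention-arm loss removes about a third to a half of the planned one-item effect, and two remove two thirds to all of it, for mean baselines between 4.5/8 and 6.5/8. Control-arm losses inflate the estimate by a similar amount. Losses at random mainly cost power.

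These sizes rest on an assumed number of missing manuscripts, assumed baselines for submitted manuscripts, and the Box 2 distributions for final scores. The effect shrinks at lower baselines and is nil if no score is missing.

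**What to change.** - Make the baseline-adjusted complete-case regression the primary analysis.
- Report imputation by b (the completeness of the only existing version) and by 1 − b as sensitivity analyses. Imputation by b should not be primary either: with baselines two items lower its power is 54% with 2 missing.
- Report rejections and non-returns separately, by arm.
- State that complete case conditions on a post-randomisation decision by an unblinded editor, and can be biased if rejection depends on arm and reporting quality.
- In Box 3, set na and nb so that their sum is the number of manuscripts analysed.
- Reconcile Assignment of interventions with Outcomes and Statistical methods, so that the masked assessors score the first submitted version of every randomised manuscript. Confirm that b and the baseline consistency covariate are the same quantity.

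The cost is SAP wording, two values in Box 3, one added sensitivity analysis, and assessor time for the first versions of manuscripts never revised. The price in inference is that the primary result is restricted to manuscripts with a revision and is not protected against arm-dependent rejection. The by-arm counts and the two sensitivity analyses show how far that matters.
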